3.2. Secondary Endpoint(s)

- The secondary endpoints include the standard safety endpoints, namely, adverse events (AEs), clinical laboratory tests, vital signs (including blood pressure and pulse rate), and 12-lead electrocardiograms (ECG). These will be further described in [Section 3.5](#).
- PF-06865571 C_{max} , AUC_{tau} , T_{max} , C_{min} , CL/F, and PTR on Day 14, as permitted by the data,

The PK parameters for PF-06865571 will be derived from the concentration-time profiles as data permit. The various PK parameters to be assessed in this study, their definition and method of determination are outlined in Table 2. Actual PK sampling times will be used in the derivation of PK parameters.

Table 2. Definition of Steady State (Day 14) Plasma PK Parameters for PF 06865571

Parameter	Definition	Method of Determination
AUC_{tau}	Area under the plasma concentration-time profile from time zero to time tau (τ), the dosing interval	Linear/Log trapezoidal method
C_{max}	Maximum plasma concentration during the dosing interval	Observed directly from data
T_{max}	Time for C_{max}	Observed directly from data as time of first occurrence
CL/F	Apparent clearance	Dose/ AUC_{tau}
C_{min}	Minimum plasma concentration during the dosing interval	Observed directly from data
PTR	Peak-to-trough ratio	C_{max}/C_{min}

CCI

CCI

3.4. Baseline Variables

Baseline variables are those collected on Day 1 prior to dosing or before Day 1. The demographic data of age, race, weight, and body mass index will be summarized by sex at birth and treatment in accordance with the sponsor reporting standards. Ethnicity will not be summarized. The number and proportion of subjects enrolled in each study site will also be presented.

In this study subjects will be stratified at randomization based on the presence or absence of Type 2 Diabetes Mellitus (T2DM) and by the MRI-PDFP liver fat categories obtained during Visit 3 (Screen 3) listed below:

- Screening liver fat $\geq 6\%$ and $< 10\%$;
- Screening liver fat $\geq 10\%$.

Both of these stratification variables will be used as covariates in the efficacy analysis. For baseline diabetic status, data will be obtained from the case report forms (CRFs). Even though baseline liver fat was used as a binary variable for stratification purposes, it will be used as a continuous covariate in the efficacy analysis in order to maximize the utility of information. If there is substantial imbalance in the number of subjects enrolled in each site then study site will be considered to be included as a potential covariate. If included as a covariate sites enrolling less than 6 subjects will be pooled.

3.5. Safety Endpoints

The following data are considered in standard safety summaries (see protocol for collection days and list of parameters):

- AEs;
- Laboratory data;
- Vital signs data;
- ECG results.

3.5.1. Adverse Events

For serious adverse events (SAEs), the reporting period to Pfizer or its designated representative begins from the time that the subject provides informed consent, which is obtained prior to the subject's participation in the study, ie, prior to undergoing any study-related procedure and/or receiving IP, through and including 28 calendar days after the last administration of the IP.

Similarly, the time period for collecting AEs (“active collection period”) for each subject begins from the time the subject provides informed consent. The AEs occurring following start of the double-blind randomized treatment will be counted as treatment emergent. The AEs occurring prior to the double-blind randomized treatment intake will be listed.

The 3-Tier approach will not be used to summarize the AEs due to the small sample size.

3.5.2. Laboratory Data

Safety laboratory tests will be performed as described in the protocol.

To determine if there are any clinically significant laboratory abnormalities, the haematological, clinical chemistry (serum) and urinalysis safety tests will be assessed against the criteria specified in the sponsor reporting standards. The assessment will take into account whether each subject’s baseline test result is within or outside the laboratory reference range for the particular laboratory parameter.

Baseline is defined as the result closest *prior to* dosing on Day 1.

3.5.3. Vitals

Supine blood pressure and pulse rate measurements will be taken at time points detailed in the Schedule of Activities given in the protocol.

Baseline is defined as the result closest *prior to* dosing on Day 1. The following vital signs endpoints will be determined for each subject:

- The maximum decrease and increase from baseline over all measurements taken post dose for systolic and diastolic blood pressures.
- The maximum increase and decrease from baseline over all measurements taken post dose for pulse rate.

The maximum increase from baseline will be calculated by first subtracting the baseline value from each post dose measurement to give the change from baseline. The maximum of these values over the respective period will then be selected, except in the case where a subject does not show an increase. In such an instance, the minimum decrease should be taken. Similarly, the maximum decrease from baseline will be determined by selecting the largest negative value of the changes from baseline. In cases where a subject does not show a decrease, the minimum increase should be taken.

3.5.4. ECGs

Triplicate 12-lead ECGs will be obtained on all subjects at times detailed in the Schedule of Activities given in the protocol. Average of the triplicate will be utilized in all analysis. Baseline is defined as the result closest *prior to* dosing on Day 1.

The QT, QTcF, heart rate, QRS and PR will be recorded at each assessment time. If not supplied, QTcF will be derived using Fridericia’s heart rate correction formula:

$$QTcF = QT / (RR)^{1/3} \quad \text{where } RR = 60/HR \text{ (if } RR \text{ is not provided)}$$

The maximum absolute value (post dose) and the maximum increase from baseline for QTcF, heart rate, PR and QRS, will be determined by study day for each subject.

The maximum increase from baseline will be calculated by firstly subtracting the baseline value from each post dose measurement to give the change from baseline. The maximum of these values over the respective period will then be selected, except in the case where a subject does not show an increase. In such an instance, the minimum decrease should be taken preserving the sign of change.

3.5.5. Non-Standard Safety Assessments

Serum creatinine (Scr) and serum cystatin C will be collected as part of the safety panel. From Scr estimated glomerular filtration rate (eGFR) will be calculated, if not supplied, using the modification of diet in renal disease (MDRD) equation provided below.

MDRD Formula:

$$GFR \text{ (mL/min/1.73 m}^2\text{)} = 175 \times (S_{cr})^{-1.154} \times (Age)^{-0.203} \times (0.742 \text{ if female}) \times (1.212 \text{ if black})$$

GFR will be estimated from the cystatin C using the CKD-Epi-Cystatin C equation provided below:

- For serum cystatin C (Scys) ≤ 0.8 mg/L:

$$eGFR \text{ (mL/min/1.73 m}^2\text{)} = 133 \times (Scys/0.8)^{-0.499} \times 0.996^{Age} [\times 0.932 \text{ if female}]$$

- For serum cystatin C (Scys) > 0.8 mg/L:

$$eGFR \text{ (mL/min/1.73 m}^2\text{)} = 133 \times (Scys/0.8)^{-1.328} \times 0.996^{Age} [\times 0.932 \text{ if female}]$$

Baseline is defined as the result closest *prior to* dosing on Day 1.

4. ANALYSIS SETS

Data for all subjects will be assessed to determine if subjects meet the criteria for inclusion in each analysis population prior to unblinding and releasing the database and classifications will be documented per standard operating procedures.

4.1. Full Analysis Set

The Full Analysis Set (FAS) is defined as all randomized subjects who received at least 1 dose of randomized treatment; subjects are assigned to the randomized treatment regardless of what treatment was received. This would be the primary analysis population for all efficacy analyses.

4.2. Per Protocol Analysis Set

This will not be used in the current study.

4.3. Safety Analysis Set

All subjects who receive at least 1 dose of IP post-randomization will be included in the safety analyses and listings. All safety endpoints will be analyzed by the treatment that the subjects actually receive (for the majority of the study duration) regardless of which treatment group they are randomized. A randomized but not treated subject will be excluded from the safety analyses. A treated but not randomized subject will be reported under the treatment actually received.

For AE reporting all subjects providing informed consent regardless of their randomization status will be included.

4.4. Other Analysis Sets

The PK concentration population will be defined as all randomized subjects who received at least 1 dose of PF-06865571 and in whom at least 1 plasma PK concentration value is reported. The PK parameter analysis population will be defined as all randomized subjects who received at least 1 dose of PF-06865571 and who have at least 1 of the PK parameters of interest calculated.

5. GENERAL METHODOLOGY AND CONVENTIONS

The analysis will be performed after database release following last subject last visit.

5.1. Hypotheses and Decision Rules

The following null hypotheses will be tested for each endpoint:

1. 300 mg PF-06865571 Q12H is equal in effect to placebo.
2. 50 mg PF-06865571 Q12H is equal in effect to placebo.

The alternative hypotheses corresponding to the above null hypotheses will be the following 2-sided hypotheses:

1. The effect of 300 mg PF-06865571 Q12H is different from the effect of placebo.
2. The effect of 50 mg PF-06865571 Q12H is different from the effect of placebo.

The Type I error rate (α -level) used with the decision rule for the primary objective is 10% (1-sided). No adjustment for multiple comparisons will be made.

Interim analyses may be performed to assess efficacy and/or safety after at least 50% of the planned subjects, ie, approximately 21 subjects, complete the study. Interim analysis results may be used for internal business decisions regarding future study planning or stopping for futility. As such no adjustment in the Type I error rate is proposed.

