5.2. General Methods

Descriptive Statistics

Descriptive statistics, including the sample size, mean, standard deviation, median, minimum, and maximum values, will be provided for continuous endpoints. Some measures will be summarized using graphical representations by treatment and study day of visit, where appropriate.

Analysis of Covariance (ANCOVA)

The ANCOVA model will be used with continuous endpoints for landmark (single time point) analyses. The model will include treatment group as fixed effect, baseline value of the endpoint being analyzed, baseline whole liver PDFF and baseline diabetes status as covariates. If there is substantial imbalance in the number of subjects enrolled in each site then study site and interaction of study site with treatment will be considered to be included as potential covariates for the analysis of primary endpoint only. If included as a covariate, sites enrolling less than 6 subjects will be pooled. The number of covariates may be reduced to improve model fit. Estimates of treatment effects will be assessed using LSMs and CIs. Estimates of the mean differences between each active dose and placebo, and the corresponding 80% CI will be obtained from the model. Comparison of each PF-06865571 dose with the placebo will be performed at a Type I error rate of 10% (1-sided). If there are major deviations from the statistical assumptions underlying this model then alternative transformations (eg, log) or non-parametric analyses may be presented. Justification for any alternative to the planned analysis will be given in the study report.

Non-parametric Analysis

If the data have many outliers even after the log-transformation the following non-parametric analysis will be performed instead of the linear model. An outlier will be defined as any datapoint falling outside of $3.5 \times$ standard deviations \pm the median. Additional evaluative statistics will be conducted to explore the nature of the outliers in order to determine the appropriateness of a parametric analysis.

For group medians 80% CIs will be presented. In addition the 80% CIs will also be presented for differences in group medians from placebo group median. The method of McGill, Tukey, and Larson¹ will be employed to calculate the CI for the difference in treatment group medians.

CCI [REDACTED]

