6. ANALYSES AND SUMMARIES

6.1. Primary Endpoint: Whole Liver PDFF

6.1.1. Primary Analysis

- **Analysis endpoint:** Whole liver PDFF.
- **Analysis time points:** Day 15.
- **Analysis population:** Full Analysis set
- **Analysis methodology:** Natural log-transformed individual relative change (RC) from baseline to Day 15 in whole liver PDFF will be analyzed using the ANCOVA. Log-transformed baseline will be the covariate. The model will include natural log-transformed baseline whole liver PDFF and diabetes status. If there is substantial imbalance in the number of subjects enrolled in each site then study site and interaction of study site with treatment will be considered to be included as potential covariates.

Reporting results:

- **Raw data:** The sample size, mean, standard deviation, median, minimum and maximum at baseline and Day 15 visit will be presented for each treatment arm.
- **%CBL:** The sample size, mean, standard deviation, median, minimum and maximum will be presented for each treatment arm at Day 15. The LSMs and their 80% CI will be exponentiated to provide estimates of the RC which will be converted to percent change as follows:

$$\text{Percent change} = 100 * (\text{RC} - 1).$$

The LSMs of the percent change from baseline with the 80% CIs for each treatment group and the LSMs of the percent change from placebo with the 80% CIs for each of the PF-06865571 groups and the 2-sided p-values will be presented.

Figures

- Whole liver PDFF - Bar chart of the model-derived least square means for all treatment groups including the placebo group with 80%CI will be provided for Day 15 with treatment group on the X-axis.
- Whole liver PDFF - Bar chart of the placebo-adjusted least square means with 80%CI for the two PF-06865571 treatment groups will be provided for Day 15 with dose on the X-axis.

- Whole liver PDFF - Box and whisker plots for individual percent change from baseline versus treatment will be presented and overlaid with arithmetic means.

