6.1.2. Sensitivity/Robustness Analyses

- **Analysis endpoint:** Whole liver PDFF.
- **Analysis time points:** Day 15.
- **Analysis population:** Full Analysis set.
- **Analysis methodology:** %CBL to Day 15 in whole liver PDFF will be analyzed using the ANCOVA. The model will include baseline whole liver PDFF and diabetes status. If there is substantial imbalance in the number of subjects enrolled in each site then study site and interaction of study site with treatment will be considered to be included as potential covariates.

Reporting results:

The LSMs, 80% CI for the LSMs, difference between the LSM of each treatment group and the placebo group, and the corresponding 80% CI and the 2-sided p-values will be presented for whole liver PDFF.

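### Do the 2-sided hypotheses in SAP 5.1 undermine the 1-sided 10% decision rule for the primary endpoint?

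*SAP*

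**What the plan says.** SAP 5.1 opens with a general statement, "The following null hypotheses will be tested for each endpoint", and lists one null hypothesis per dose: equality with placebo. It continues, "The alternative hypotheses corresponding to the above null hypotheses will be the following 2-sided hypotheses", and words each alternative as a difference from placebo without a direction. The next paragraph fixes the level for the "decision rule for the primary objective is 10% (1-sided"), with no multiplicity adjustment.

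SAP 5.2, under ANCOVA, says "Estimates of treatment effects will be assessed using LSMs and CIs", asks for 80% intervals for each dose against placebo, and adds "Comparison of each PF-06865571 dose with the placebo will be performed at a Type I error rate of 10% (1-sided"). Protocol 9.2.1 gives the same level and the same 80% interval. Protocol 9.1 bases the sample size on a 1-sided error of 0.1 and a 25% mean reduction relative to placebo.

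On reporting, SAP 6.1.1 asks for percent change from placebo with 80% intervals "for each of the PF-06865571 groups and the 2-sided p-values will be presented". SAP 6.1.2, the sensitivity analysis, asks for "the corresponding 80% CI and the 2-sided p-values will be presented for whole liver PDFF". Neither section gives a cut-off for the p-value.

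On secondary endpoints, SAP 3.2 says "The secondary endpoints include the standard safety endpoints" and adds Day 14 PK parameters. SAP 6.2 summarises PK descriptively by dose. Protocol 9.3 says placebo PK samples are not routinely analysed. SAP 6.6 gives safety summaries, some with 80% or 90% intervals for differences from placebo, and no p-values.

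**The concern.** A section headed hypotheses and decision rules should state a hypothesis that matches its rule. Here the alternative is 2-sided and the error rate 1-sided, and no sentence in the section says which direction counts. A reader who takes the 2-sided wording, the figure of 10% and the 2-sided p-value from SAP 6.1.1 could put them together and compare that p-value with 0.10. A result favouring active with a 2-sided p between 0.10 and 0.20 would then be described as missing a criterion it had met. A 2-sided p-value also does not show by itself which arm is favoured.

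The scope also looks too wide. Taken literally, testing every endpoint for equality with placebo would include plasma exposure, which cannot be compared with placebo, and safety endpoints for which no test is planned.

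**Working it through.** **Inputs.** From protocol 9.1: 25% reduction versus placebo, SD of the log relative change 0.36, 1-sided error 0.10, 42 completers. With 1:1:1 allocation (protocol 3.1) that is 14 per arm. Two choices of degrees of freedom are shown: 26 (two arms of 14, 28 − 2) and 37 (42 subjects less 5 ANCOVA parameters: intercept, two treatment terms, diabetes status, log baseline).

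**Step 1: reproduce the stated power.**

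- Effect on the log scale: −ln(0.75) = 0.2877
- Standard error: 0.36 × √(2/14) = 0.1361
- Noncentrality: 0.2877 / 0.1361 = 2.114
- Critical t, 1-sided 0.10: 1.315 (df 26), 1.305 (df 37)
- Power: 78.8% (df 26), 79.1% (df 37); 79.8% by the normal approximation

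This agrees with the protocol's 79%, so the sample size was built on the 1-sided 10% rule.

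**Step 2: translate the rule into the planned output.** The 2-sided p at the 1-sided 0.10 critical value is 2 × 0.10 = 0.20. The upper limit of the 80% interval is estimate + t × SE with the same t, so that limit is below zero exactly when the 1-sided p is below 0.10.

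| Observed result | Reduction vs placebo (df 26 / df 37) | Printed 2-sided p | 80% CI, percent change |
|---|---|---|---|
| Rule just met, 1 − exp(−t × SE) | 16.4% / 16.3% | 0.20 | −30.1% to 0 / −29.9% to 0 |
| Design effect observed | 25% | 0.044 / 0.041 | −37.3% to −10.3% / −37.2% to −10.4% |

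A 2-sided test at 0.20 has the same critical value and the same power as the 1-sided test at 0.10. Under the design effect, the chance of a rejection in the wrong direction is about 0.04%.

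**Step 3: size of the misreading.** If the 2-sided p were compared with 0.10, critical t at df 37 would be 1.687. The smallest qualifying reduction would be 1 − exp(−1.687 × 0.1361) = 20.5%, and power would be 66.7% (68.1% by the normal approximation).

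**Step 4: does any text support that misreading?** The level is given in four places: protocol 9.1, protocol 9.2.1, SAP 5.1 and SAP 5.2. All four say 1-sided 10%. Protocol 9.2.1 and SAP 5.2 pair it with an 80% interval; a 2-sided 10% rule would go with a 90% interval. No section states a 2-sided 10% rule. The direction is fixed by the reduction on which protocol 9.1 is powered.

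**Step 5: scope of the hypotheses.** SAP 6.2 and protocol 9.3 leave no route to a PK test against placebo, and SAP 6.6 asks for no safety p-values. The phrase therefore most plausibly covers the continuous endpoints analysed by the ANCOVA of SAP 5.2. Apart from the primary, these probably sit in SAP 3.3 and 6.3, whose content is blacked out. If some of them may move either way, a single shared statement has to be non-directional. Protocol 1.3.1.1, for example, mentions a possible mild rise in glucose and insulin.

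**The case for a change.** The strongest case for acting is that the correction costs a few sentences and changes no output: word the primary alternative as a Day 15 ratio below 1, and say in SAP 6.1.1 that the rule corresponds to a 2-sided p of 0.20 with the estimate favouring active. A formal hypothesis statement should not rely on other sections to supply its direction, and the gap between 79% and about 67% power shows that the misreading would matter if someone made it.

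Part of this stands. The wording in SAP 5.1 is untidy, and the printed p-value has no stated link to the rule. But the misreading requires setting aside the sentence that follows the alternatives, the same level in SAP 5.2 and twice in the protocol, and the 80% interval printed beside the p-value. Halving a 2-sided p and checking its sign is routine. The case is weaker for the secondary endpoints, where the analysis sections already settle that no test is done. It is weakest for SAP 6.1.2: a threshold there would give a sensitivity analysis a success criterion, although SAP 5.1 ties the decision rule to the primary objective.

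**Conclusion.** No change is needed. SAP 5.1 gives general 2-sided alternatives and then a specific 1-sided 10% rule for the primary objective, and the specific rule governs. An analyst following the plan declares success for a dose when the upper 80% limit for percent change versus placebo is below zero, which is the same as a 2-sided p below 0.20 favouring active. Under the design assumptions this corresponds to an observed reduction of a little over 16%, with power of about 79%. Rewording would leave the sample size, model, interval level, estimates and conclusion exactly as they are.

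This rests on 14 completers per arm, a log-scale SD of 0.36, and the 1-sided 10% rule being applied as consistently as it is written. Whether the general statement suits the other endpoints cannot be judged, because those sections are blacked out.

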5.2. General Methods

Descriptive Statistics

Descriptive statistics, including the sample size, mean, standard deviation, median, minimum, and maximum values, will be provided for continuous endpoints. Some measures will be summarized using graphical representations by treatment and study day of visit, where appropriate.

Analysis of Covariance (ANCOVA)

The ANCOVA model will be used with continuous endpoints for landmark (single time point) analyses. The model will include treatment group as fixed effect, baseline value of the endpoint being analyzed, baseline whole liver PDFF and baseline diabetes status as covariates. If there is substantial imbalance in the number of subjects enrolled in each site then study site and interaction of study site with treatment will be considered to be included as potential covariates for the analysis of primary endpoint only. If included as a covariate, sites enrolling less than 6 subjects will be pooled. The number of covariates may be reduced to improve model fit. Estimates of treatment effects will be assessed using LSMs and CIs. Estimates of the mean differences between each active dose and placebo, and the corresponding 80% CI will be obtained from the model. Comparison of each PF-06865571 dose with the placebo will be performed at a Type I error rate of 10% (1-sided). If there are major deviations from the statistical assumptions underlying this model then alternative transformations (eg, log) or non-parametric analyses may be presented. Justification for any alternative to the planned analysis will be given in the study report.

Non-parametric Analysis

If the data have many outliers even after the log-transformation the following non-parametric analysis will be performed instead of the linear model. An outlier will be defined as any datapoint falling outside of $3.5 \times$ standard deviations \pm the median. Additional evaluative statistics will be conducted to explore the nature of the outliers in order to determine the appropriateness of a parametric analysis.

For group medians 80% CIs will be presented. In addition the 80% CIs will also be presented for differences in group medians from placebo group median. The method of McGill, Tukey, and Larson¹ will be employed to calculate the CI for the difference in treatment group medians.

CCI [REDACTED]

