9.1. Sample Size Determination

Approximately 15 subjects per arm are planned in this study for a total of approximately 45 subjects. Assuming an approximate 5% premature withdrawal rate, this will ensure a minimum of 42 subjects complete the study. With this sample size the power to detect a 25% mean reduction in MRI-PDFP relative to placebo is at least 79% using a 1-sided Type I error rate of 0.1. This calculation assumes the pooled SD of the log-relative change of 0.36 (based on an internal study).

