9.2.1. Analysis of the Primary Endpoint

The primary endpoint will be the relative change from baseline at Day 15 in whole liver PDFP. Baseline will be the closest measurement prior to first dose on Day 1. An analysis of covariance (ANCOVA) will be performed on log-transformed relative change with treatment and baseline diabetic status as factors, log-transformed baseline whole liver PDFP value as a covariate. Estimates of the mean relative changes between each active dose and placebo at Day 15, and the corresponding 80% confidence interval (CI) will be obtained from the model. Each comparison of PF-06865571 dose with the placebo will be performed at a Type I error rate of 10% (1-sided). No adjustment for multiple comparisons will be made. If the model does not fit the data group medians and their differences from the placebo median will be presented. The details will be provided in the SAP.

Descriptive summaries of the observed values and percent change from baseline in whole liver PDFP for each treatment group will also be produced.

CCI

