6.6.5. Non-standard Safety Analysis

Serum Creatinine, Serum Cystatin C and Associated eGFRs

Absolute values and changes from baseline in serum creatinine, serum cystatin C, eGFRs obtained from serum creatinine and cystatin C will be summarized by treatment and day. Mean absolute values of all four parameters will be plotted separately against study day. On each plot there will be 1 line for each treatment, all treatments on the same plot including the placebo. Mean changes from baseline in eGFRs will also be plotted against study day.

Liver Function Tests

Raw values, change and %CBL in ALT, AST, Total Bilirubin, GGT, and alkaline phosphatase will be summarized by treatment at all relevant collection time points including follow-up. For %CBL group medians and differences in group medians from placebo with 80% CIs will be presented. Line plot of medians with 80% CIs for all treatment groups including the placebo group with study day on X-axis will be provided. Three lines corresponding to the 3 treatment groups will be overlaid on the same plot.

Body Weight

Raw values, change and %CBL in body weight will be summarized by treatment at all relevant collection time points including follow-up. For %CBL group medians and differences in group medians from placebo with 80% CIs will be presented. Line plot of medians with 80% CIs for all treatment groups including the placebo group with study day on X-axis will be provided. Three lines corresponding to the 3 treatment groups will be overlaid on the same plot.

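### If outliers trigger the fallback, the adjusted primary ANCOVA becomes an unadjusted difference of medians: a robust ANCOVA or Hodges-Lehmann interval would be a cheap gain in power

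*SAP*

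**What the plan says.** SAP 6.1.1 analyses log relative change in whole liver PDFF at Day 15 by ANCOVA with log baseline PDFF and diabetes status in the model. SAP 3.4 states that both stratification variables enter the efficacy analysis as covariates, with liver fat kept continuous. SAP 5.1 sets a 1-sided 10% error rate for the primary objective, and the 80% confidence interval is the interval that matches it.

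SAP 5.2 (Non-parametric Analysis) replaces the linear model if many outliers remain after log transformation. Group medians get 80% intervals, and "In addition the 80% CIs will also be presented for differences in group medians from placebo group median". The method is cited as McGill, Tukey and Larsen; the visible text gives no formula, constant, quartile definition or analysis scale. Protocol 9.2.1 has a similar provision: "If the model does not fit the data group medians and their differences from the placebo median will be presented".

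SAP 6.6.5 uses the same kind of summary routinely for liver tests and body weight: "For %CBL group medians and differences in group medians from placebo with 80% CIs will be presented".

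**The concern.** The point is what the plan switches to, not when it switches. A difference of two sample medians uses little of the information in 14 observations per arm, and as written it has no place for baseline liver fat or diabetes status. It also supplies no test, so the 2-sided p-values promised in SAP 6.1.1 would have no defined source.

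If the fallback is used, it carries the primary conclusion of a trial whose power is only about 79% at a lenient error rate. Other outlier-resistant methods keep more of that power, and one of them keeps the covariates. The interval's real confidence level also depends on details that the SAP leaves to the software.

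**Working it through.** **Inputs (Protocol 9.1).** "Approximately 15 subjects per arm are planned in this study for a total of approximately 45 subjects"; "this will ensure a minimum of 42 subjects complete the study", so 42/3 = 14 per arm. "This calculation assumes the pooled SD of the log-relative change of 0.36". The effect is a 25% reduction, or |ln 0.75| = 0.2877 on the log scale. Stated power "is at least 79% using a 1-sided Type I error rate of 0.1".

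**The plan's own figure.** SE of a difference in means = 0.36×√(2/14) = 0.1361, and 0.2877/0.1361 = 2.114. Power = Φ(2.114 − 1.282) = 79.7%. With a t reference it is 79.1% (37 df) or 78.8% (26 df). The stated figure reproduces.

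**Assumed interval for the fallback.** The SAP prints no formula, so I took SE = 1.25×IQR/(1.35×√n) per group and difference ± 1.282×√(SE₁² + SE₂²). For normal data the IQR is about 1.35 SD, so the SE of the difference is about 1.25×0.1361 = 0.170. Power is then about Φ(0.2877/0.170 − 1.282) = Φ(0.41) = 66%.

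**Simulation at 14 per arm.** There were 40,000 or more trials per case for the median interval. The three figures in a cell are for averaged, linear-interpolation and (n+1)p quartiles.

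| Data | Coverage, % | 1-sided error, % | Power, % | Hodges-Lehmann power, % | Unadjusted t power, % |
|---|---|---|---|---|---|
| Normal | 80 / 77 / 84 | 9.7 / 11.3 / 7.7 | 66 / 70 / 62 | 76 | 79 |
| 10% contamination at 5×SD | 82 / 78 / 86 | 9.3 / 11.2 / 7.4 | 60 / 64 / 55 | 66 | 52 |
| 20% contamination at 4×SD | 83 / 79 / 87 | 8.9 / 10.7 / 6.7 | 54 / 58 / 48 | 58 | 45 |
| t with 3 df, SD 0.36 | 83 / 79 / 87 | 8.5 / 10.3 / 6.4 | 89 / 91 / 86 | 92 | 83 |
| Laplace, SD 0.36 | 86 / 82 / 89 | 7.3 / 9.0 / 5.3 | 84 / 87 / 80 | 86 | 80 |

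The exact Hodges-Lehmann interval at 14 per arm has confidence 80.6%, so its 1-sided error is 9.7%.

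**Sensitivity of coverage.** Coverage also depends on the shape of the data and on the final count. Uniform data give 77 / 74 / 80% and a two-peaked mixture gives 74 / 70 / 77%. For normal data, 13 per arm gives 75 / 75 / 83% and 15 per arm gives 83 / 76 / 83%.

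**Huber ANCOVA (3,000 trials per case).** With baseline unrelated to response, power is 75% on normal data and 66% with 10% contamination at 5×SD. With an assumed baseline correlation of −0.4 it is 81% and 71%. The 1-sided error is 9.6-10.4%. The documents give no value for that correlation, so the second pair only illustrates what adjustment could add.

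**The case against.** The strongest reply is that the fallback is meant for data in which least squares does badly, and there it helps. With 10% contamination at 5×SD it has 55-64% power, against 52% for an unadjusted t interval. This stands: leaving least squares is sensible, and only the destination is in question.

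The margin over the alternatives is also modest. Under that contamination Hodges-Lehmann gains about 2 points over the best quartile rule and 11 over the worst. With 20% contamination at 4×SD, with t data on 3 df and with Laplace data it is within about 1 point of the best rule. This stands too, although the best rule for power (linear interpolation) runs above 10% error in most of those cases.

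Dropping the covariates does not bias the comparison: the response is already relative to baseline, and randomization is stratified on liver fat and T2DM. The SAP also calls for further evaluation of outliers and for justification of any alternative analysis in the report. The sensitivity analysis in SAP 6.1.2 keeps the covariates, but it is an ANCOVA on untransformed percent change and so is not outlier-resistant.

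A reader might infer that the 80% interval is too short at 14 per arm and that the 1-sided error therefore exceeds 10%. The documents do not support that. It is true for linear-interpolation quartiles on near-normal data (about 77% and 11%), but the other two rules give 80-84% coverage and error below 10%, and the SAP does not say which applies. A reader might also set the fallback's power against the planned 79% and blame the whole gap on the method. The 79% assumes SD 0.36 without outliers, so part of any shortfall in a triggering case comes from the outliers themselves.

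**Conclusion.** The concern holds as a cheap improvement to a conditional analysis. The fallback gives up the covariates that SAP 3.4 commits to, and it has less power than Hodges-Lehmann on normal data (62-70% against 76%) and with 10% contamination at 5×SD (55-64% against 66%). At heavier tails there is little or no gain over the best quartile rule. Covariate adjustment would add more only if baseline liver fat or diabetes status predicts response.

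The interval's actual level is unspecified rather than shown to be wrong: about 77-84% for normal data and 79-89% for the heavy-tailed cases run, with values down to 70% for a two-peaked distribution. All figures for the median interval rest on the assumed standard error, 14 completers per arm and log SD 0.36.

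For liver tests and body weight, median differences are the only between-arm inference in the visible text, and redacted text could hold more. These are safety summaries with no decision rule attached, so little is at stake there.

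**What to change.** In SAP 5.2 and Protocol 9.2.1, define the fallback as a robust ANCOVA (Huber M-estimation) on log relative change with the same terms as SAP 6.1.1, and report the 80% interval back-transformed to percent change. If a simpler method is preferred, use the Hodges-Lehmann shift on the log scale with its rank-based 80% interval, which gives up the covariates but holds its level. Show group medians descriptively in either case. If the median-difference interval is kept, state its constant, quartile definition and analysis scale.

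Using Hodges-Lehmann differences in SAP 6.6.5 is optional.

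The cost is wording and a standard procedure; no new data are needed. There are two downsides: the estimate is a location shift and not literally a difference of medians, and Huber inference is approximate at this sample size.
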